Women's First Gastrointestinal Activation Post-elective Cesarean Birth During Post-partum Hospitalization: A Comparison of Paula Method (the Circular Exercises Method) to Standard Care

NCT03761147

Document Date: August 7, 2017

Protocol

Caesarean section births constitute a significant percentage of all births in the western world and since the 1980s, there has been a constant rise. Caesarean section births can be associated with various post-operative complications, including poor peristalsis. In the hospital where this study was performed, the main treatment to accelerate post-operative bowel movement include early water drinking, early ambulation, and the use of laxatives. In this study these modalities are defined as the standard therapy.

Since the standard methods are not always effective and not suitable for all women who underwent a Caesarean delivery, there is a need for finding alternative treatments to accelerate bowel function. The method examined in this study is called "the Paula method for the training of ring muscles". According to this method, the contracting and releasing of the one ring muscle causes other involuntary ring muscles to be activated as well, including intestinal system muscles.

The purpose of this study is to examine the effectiveness of the Paula Method compared with the standard treatment offered to women after elective Caesarean delivery. In our study, gastrointestinal activation was defined as the initial appearance of intestinal sounds, first flatus passage and first defecation after the surgery.

This is randomized controlled clinical study examined the effectiveness of performing training according to the "Paula Method" to accelerate gastrointestinal activity in women after elective Caesarean section, compared with the standard treatment. The study included 64 women following elective Caesarean section

performed under regional anesthesia. The participants were randomized on a 1:1 basis into a training group and a control group after signing the informed consent document. The women in the training group performed ring muscle training according to the Paula Method five minutes of exercise six times a day and those in the control group were treated with the standard protocol. During the experiment, data was collected on the timing of appearing the first bowel sounds, first flatus passage and first defecation after surgery. In addition, demographic data as well information regarding pain medications used during the hospitalization and course of the admission were collected.

All data collected during the study were analyzed using SPSS software. With the help of the software, an analysis of the demographics and health of the sample was performed. In addition, the mean time and standard deviations of first bowel sounds, first flatus passage and first defecation after surgery were obtained from the analysis, as well as frequency of postoperative complications in each group and other data. Based on these data, conclusions were drawn about the efficacy of the two intervention methods studied in this study in the operation of the gastrointestinal tract after cesarean section. The effect of taking different types of pain medication on the duration of hospitalization in both groups was examined using the Pearson correlation and the results were confirmed by T-test.

References

doi:10.1185/03007995.2015.1005833

Garbourg, P. (1992). Self healing: The secret of the ring muscles. Peleg Publishers & Balaban Publishers, p. 17.

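### Does silence on whether the training group also received standard therapy call for a change to the plan?

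*Combined protocol and SAP*

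**What the plan says.** The opening paragraph of the Protocol describes local practice: "the main treatment to accelerate post-operative bowel movement include early water drinking, early ambulation, and the use of laxatives". It adds: "In this study these modalities are defined as the standard therapy". The title announces "A Comparison of Paula Method (the Circular Exercises Method) to Standard Care". The background argues that "there is a need for finding alternative treatments to accelerate bowel function", and the purpose paragraph sets out to examine "the effectiveness of the Paula Method compared with the standard treatment offered to women after elective Caesarean delivery".

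The arms are described in one sentence of the paragraph on randomization. The training group exercised for "five minutes of exercise six times a day and those in the control group were treated with the standard protocol". No other sentence assigns standard therapy to the training group or withholds it, and the rest of the document is a reference list.

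On treatment data, the same paragraph says that, besides the three event times and demographics, "information regarding pain medications used during the hospitalization and course of the admission were collected". Laxatives appear only in the definition of standard therapy. In the analysis paragraph, "the mean time and standard deviations of first bowel sounds, first flatus passage and first defecation after surgery were obtained from the analysis", together with complication frequencies and other unspecified data, and efficacy conclusions about both methods are drawn from these. No between-arm difference or interval is named for the three event times. The only tests named, a Pearson correlation and a t-test, concern pain medication and length of stay.

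**The concern.** What each arm received decides what a difference means. Suppose the training arm has earlier first defecation. If the exercises replaced drinking, ambulation and laxatives, the trial shows they did better than standard therapy. If they were added, it shows they helped on top of it. A null result is equally open to two readings: under replacement a reader may be tempted to say the exercises match standard therapy, and under add-on that they contribute nothing.

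Laxatives sharpen the worry. They are part of the defined standard therapy and bear directly on first defecation, yet their use by arm is not a named data item or analysis. On a first reading, a reader cannot tell which question the trial answered, and an element that could drive one of the three outcomes seems to be left untracked.

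**Working it through.** **Reading the text.** The wording pointing each way, set side by side:

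- *Towards replacement:* the title compares the method with standard care; the background looks for alternatives to methods described as not always effective or suitable; the purpose and design sentences both compare the method with the standard treatment; the arm description contrasts exercises with the standard protocol; the analysis paragraph treats the arms as a pair of intervention methods.
- *Towards add-on:* no phrase says so. The support is indirect. The modalities were the hospital's main treatment, offered to women after this operation, and nothing says they were withheld.

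The text leans towards replacement without settling it. This is silence on one point. No two passages contradict each other.

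**Does the ambiguity alter the analysis?** Inputs: 64 women (Protocol, design paragraph) and 1:1 allocation (randomization paragraph), so 64/2 = 32 per arm if the arms are equal. The documents give no SD, alpha or power, so I work in SD units with a normal-theory interval, both assumed.

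- 95% half-width for a difference in means = t(0.975, 62) × sqrt(2/32) = 1.9990 × 0.25 = 0.4997 SD.
- Unequal arms barely matter: 0.5007 SD for 30/34 and 0.5037 SD for 28/36.

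Nothing in this formula depends on whether standard therapy was replaced or supplemented. The ±0.50 SD is a property of the sample size. It is a fair warning against reading a null result as equality, but it does not size this gap.

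**Would a laxative table settle the matter?** The 95% half-width for a difference in proportions is 1.96 × sqrt[(p1(1−p1) + p2(1−p2))/32]. All values of p are assumed:

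| Use in the two arms | Half-width (percentage points) |
|---|---|
| 10% and 10% | 1.96 × sqrt(0.18/32) = 14.7 |
| 20% and 20% | 1.96 × sqrt(0.32/32) = 19.6 |
| 50% and 50% | 1.96 × sqrt(0.50/32) = 24.5 |
| 0% and 80% | 1.96 × sqrt(0.16/32) = 13.9 |

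No single range holds without assuming the pattern of use. Under replacement, use is meant to differ between arms, so showing equality is beside the point. Under add-on, use arises after randomization and would be described, not adjusted for. In neither case would the table change the primary contrast. Such records may exist under the course of the admission or the unspecified other data, but the documents do not say.

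**The case for a change.** The strongest argument for acting is that comparative phrases describe a contrast without listing what a woman in the training group received. Full replacement would mean no early water, no early ambulation and no laxatives in one arm, and the document never says this. A mixture is also possible, for example drinking and ambulation for everyone with laxatives for controls only. Efficacy conclusions are promised, and one clarifying sentence would be cheap.

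Much of this stands. The gap is real, the mixture cannot be excluded, and the wording of the conclusion should follow what the arms actually received. It remains a point of description: the allocation, the outcomes and the as-allocated comparison stay the same whichever answer is given. Group means and SDs are already part of the analysis, and an analyst would ordinarily add the difference and its interval.

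Two further arguments do not stand. Opposite recommendations arise only if someone words a null result as equality or as no added effect, and the documents propose neither. How wards would respond is a prediction the documents do not support. Finally, the public version omits the consent pages, which may describe the arms, so absence from this text is weak evidence that the study never specified it.

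**Conclusion.** No change to the plan follows. The Protocol leaves one descriptive fact unstated, its wording leans towards replacement, and a sensible report fills the gap by saying what each arm received and phrasing the conclusion to fit. The randomized contrast is valid under either reading. No bias, loss of power or error rate can be attributed to the ambiguity, and the ±0.50 SD precision (32 per arm, normal-theory interval) is the same in both cases.

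Two limits apply. I cannot say from the documents which reading is correct, and I make no judgement on which care either arm should have had. Means for first defecation also presume that the event was observed before discharge. The documents do not say whether any woman left earlier, but that question is separate and arises equally under both readings.

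### The efficacy conclusion rests on means and SDs of three first-event times, with no named between-group comparison, no stated end of observation and no rule for a woman discharged event-free

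*Combined protocol and SAP*

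**What the plan says.** The document is one short combined protocol and analysis plan with unnumbered paragraphs, written in the past tense.

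- **Outcomes.** Gastrointestinal activation is defined by three first events after surgery: bowel sounds, flatus and defecation. On collection: "During the experiment, data was collected on the timing of appearing the first bowel sounds, first flatus passage and first defecation after surgery".
- **Analysis of these outcomes.** The data-analysis paragraph says that "the mean time and standard deviations of first bowel sounds, first flatus passage and first defecation after surgery were obtained from the analysis". It then adds complication rates and unspecified further items, and rests the efficacy conclusion on the whole set: "as well as frequency of postoperative complications in each group and other data. Based on these data, conclusions were drawn about the efficacy".
- **Named tests.** They appear only in the last sentence of that paragraph, which deals with analgesic type and length of stay: "on the duration of hospitalization in both groups was examined using the Pearson correlation and the results were confirmed by T-test".
- **Observation window.** The only hint is the title: "First Gastrointestinal Activation Post-elective Cesarean Birth During Post-partum Hospitalization".
- **Might some women be event-free?** The background points both ways. It says "Since the standard methods are not always effective and not suitable for all women who underwent a Caesarean delivery", but it lists "early water drinking, early ambulation, and the use of laxatives" as the standard therapy.
- **Discharge data.** "information regarding pain medications used during the hospitalization and course of the admission were collected", and duration of hospitalization was analysed, so discharge times should be on file.

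**The concern.** There are two gaps, and they differ in kind.

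**Unconditional.** The efficacy conclusion needs a comparison of the arms on these three times, and none is named: no test, interval or model. This matters even with complete data, because a reader cannot tell what evidence of a difference supported the conclusion.

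**Conditional.** A time to first event has no value for a woman who leaves hospital before the event. A mean can handle her in only two ways, and the plan chooses neither.

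- *Drop her.* The comparison is then between subsets selected after randomisation, and the difference can shrink or grow.
- *Substitute a value such as her discharge time.* With equal discharge timing in the arms this is close to a restricted mean, a legitimate but smaller quantity than the full mean difference. If timing differs by arm, it is biased.

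The latest of the three events is the one most exposed; early events may be untouched.

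**Working it through.** **Plan's own figures.** There is nothing to reproduce: 64 women are stated without alpha, power, effect size or SD, and no event rate, length of stay or discharge criterion is given. Everything after step 1 is illustration on assumed inputs.

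**Step 1: the missing comparison.** With 1:1 allocation, 64/2 = 32 per arm. For a common standard deviation SD, the standard error of a difference in means is SD × √(2/32) = 0.25 SD. The 95% CI half-width is about 1.96 × 0.25 = 0.49 SD. The difference detectable with 80% power (two-sided 5%, assumed) is (1.96 + 0.84) × 0.25 = 0.70 SD. Two means can therefore differ by nearly half an SD and still be compatible with no effect, so the interval is essential.

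**Step 2: dropping, when training shortens all times in proportion.** Assumed: Weibull event times T with shape k = 1.5 to 3; training times 0.75 × control times; discharge D normal, mean 84 h, SD 8 h, in both arms and independent of T. The control median is set so that a given number of 32 controls is event-free.

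- Full mean = scale × Γ(1 + 1/k)
- Mean after dropping = E[T | T < D]
- Mean after substituting = E[min(T, D)]

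Worked case, k = 2 with 4 of 32 controls event-free: the control median is 47.8 h, so the scale is 47.8/√(ln 2) = 57.4 h and the full mean is 57.4 × 0.886 = 50.9 h. The training mean is 0.75 × 50.9 = 38.2 h, so the true difference is 12.7 h. Integrating E[T | T < D] gives 44.1 h and 36.7 h, a difference of 7.4 h, which is 7.4/12.7 = 58% of the truth.

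Share of the true difference kept, over shapes 1.5 to 3:

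| Controls event-free (of 32) | Dropping | Substituting discharge time |
|---|---|---|
| 0 | 100% | 100% |
| 1 | 79-90% | 95-98% |
| 2 | 67-83% | 90-96% |
| 4 | 50-70% | 80-91% |

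Substituting stays within 2 percentage points of a restricted mean to 84 h. With a control median of 12 to 24 h, at most 1.3% of controls are event-free and dropping keeps 89-100%.

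**Step 3: the opposite direction.** Suppose training shortens only times that would fall before discharge, by a fraction δ, and a proportion p is event-free in both arms. Let m be the control mean among women with the event. The true difference is (1 − p)δm and dropping gives δm, a ratio of 1/(1 − p). With 1 of 32 event-free this is 32/31 = 103%; with 4 of 32 it is 32/28 = 114%. Substituting leaves the difference unchanged.

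**Step 4: unequal discharge and no true effect.** With k = 2 and 4 of 32 controls event-free, training women discharged 8 h earlier give false-positive rates of 7% (dropping) and 5-6% (substituting); 12 h earlier gives 10% and 6%. With 1 of 32, even a 12 h shift gives only 7% and 5%.

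**Step 5: power at 32 per arm, k = 2, 25% shortening.** With 1 of 32 controls event-free: dropping 48%, substituting 56%, log-rank 60%. With 4 of 32: 31%, 53% and 59%.

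**Step 6: a different model.** Lognormal times (control median 60 h, log-SD 0.5, time ratio 0.8, common discharge at 96 h, about 5.5 of 32 controls event-free) give a true difference of 13.5 h, 6.9 h after dropping (6.9/13.5 = 51%) and 10.0 h after substituting (74%). Power is 26%, 40% and 37% for dropping, substituting and log-rank. The loss from dropping is not specific to the Weibull model. The log-rank advantage over substituting is: scaled Weibull times have proportional hazards, which favours it.

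**The case against.** The strongest reply is that the censoring harm is hypothetical. The documents report no woman without an event. The remark that standard methods do not always work is general background, and laxatives in standard therapy point the other way. If discharge awaited the event, nobody was event-free and the bias is nil. The size and direction in the illustration depend wholly on assumed inputs: at 1 of 32 event-free, substituting loses little, and false-positive rates rise materially only with many hours' difference in discharge. The text is also a brief retrospective summary that mentions unspecified other data, so silence may be under-reporting.

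Most of this stands, and it limits the point. A reader might infer that event-free women existed and were left out, that the efficacy result is biased, or that the arms were never tested against each other. The documents support none of these: they are silent on all three.

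Two things survive. The missing between-group comparison does not depend on event-free women at all. And a mean has no place for a woman without an event time, so the count must be known before anyone can say whether the means compare the randomised groups.

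**Conclusion.** The point holds in two parts. First, and unconditionally, no between-group comparison is named for the outcomes that carry the efficacy conclusion; a difference with a 95% CI and a named test is needed whatever the event counts were. Second, and only if some woman was event-free at discharge, the mean-based analysis can mislead. Under proportional shortening with equal discharge timing, dropping keeps about 79-90% of the true difference with 1 of 32 controls event-free and 50-70% with 4 of 32. If only pre-discharge times shorten, it inflates the difference to 103% and 114% at the same counts in both arms. The documents cannot say which pattern applies, or whether either does. This is worth fixing, with medium confidence; it is not evidence that the reported conclusion is wrong.

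**What to change.** 1. State that observation ends at discharge, as the title implies, and report the number of women event-free by arm and endpoint.
2. For an endpoint with none, keep the means and SDs and add the difference with 95% CI and a named test.
3. For an endpoint with any, analyse all 64 randomised women by time from end of surgery, censored at discharge: Kaplan-Meier curves and medians by arm, a log-rank test, and a hazard ratio with 95% CI.
4. Because discharge may depend on bowel function, add a sensitivity analysis that ranks event-free women as latest, noting that it is tilted against the arm discharged earlier.
5. If the original analysis has been run, label this a reanalysis.

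**Cost.** The first step is a count. No new data are needed if discharge times are on file, and SPSS has Kaplan-Meier and Cox procedures. The downside is that results for affected endpoints are no longer simple means. A restricted mean to a fixed hour keeps the hour scale, but estimates a smaller quantity than the full mean difference.

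### The plan draws conclusions on the efficacy of two methods from per-group means, but the two-arm design supports only the difference between the arms

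*Combined protocol and SAP*

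**What the plan says.** The document has no numbered sections, so places are given by paragraph.

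- **Purpose paragraph.** The aim is relative: to "examine the effectiveness of the Paula Method compared with the standard treatment offered to women after elective Caesarean delivery". The title also describes a comparison.
- **Opening paragraph.** Standard therapy is defined as "early water drinking, early ambulation, and the use of laxatives", described as "the main treatment to accelerate post-operative bowel movement" in the study hospital. No estimate of its effect against no treatment is given.
- **Design paragraph.** Women were "randomized on a 1:1 basis into a training group and a control group". The training arm "performed ring muscle training according to the Paula Method five minutes of exercise six times a day". The comparator is active: "those in the control group were treated with the standard protocol". No untreated, sham or historical reference is described. The text does not say whether the training arm also received standard care.
- **Data-analysis paragraph.** Means and standard deviations of the times to the three bowel events are obtained, along with complication frequencies by group. On that basis "conclusions were drawn about the efficacy of the two intervention methods studied in this study". This is the only sentence that connects the bowel outcomes to a conclusion. No between-arm test, confidence interval or equivalence or non-inferiority margin is given for them. The one t-test mentioned concerns pain medication and length of stay.

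**The concern.** The conclusion sentence is wider than the objective. The objective asks whether one method does better than the other, whereas the sentence speaks of the efficacy of two methods and rests on figures computed within each arm. The mean time in one arm shows how long those women took. Without a reference it does not show how much of that time the treatment saved.

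What is at stake is the claim made if the two arms look alike. The rationale paragraph looks for alternatives to standard care. Under the present wording, two similar means could be reported as two effective methods, with Paula training as a demonstrated alternative. The trial could support neither statement. Adding a correct between-arm test would not change that, because a test of the difference still says nothing about either method against no treatment.

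**Working it through.** **Inputs.** From the document: two arms, 1:1 allocation, 64 women, an active control and no untreated reference. Assumed: exactly 32 per arm, every event observed in every woman, a common SD and two-sided alpha of 0.05. The document gives no SD, effect size, alpha, power or margin. The figure of 64 therefore cannot be reproduced, and it is not disputed here.

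**Step 1: what the arms identify.** Let U be the mean time without either method, eS the effect of standard therapy and eP the effect of Paula training. Negative values mean faster recovery.

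- If the training arm did not receive standard care, the arm means are U + eS and U + eP, and their difference is eP − eS, a replacement effect.
- If it did, the arm means are U + eS and U + eS + eA, where eA is Paula's effect on top of standard care. The difference is eA, an added effect, and eS cancels.

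In both cases there is one contrast. U is unknown, so eS cannot be separated from it.

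**Step 2: illustration for the replacement case.** This is a simulation with a normal approximation, 32 per arm and effects in SD units.

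| eS | eP | Expected difference | Rejection rate |
|---|---|---|---|
| 0 | 0 | 0 | 5% |
| −0.8 | −0.8 | 0 | 5% |
| +0.4 | +0.4 | 0 | 5% |
| 0 | −0.8 | −0.8 | 89% |
| −0.8 | −1.6 | −0.8 | 89% |

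Both methods inert, both helpful and both harmful give the same expected difference and the same rejection rate. So do the last two rows, although standard therapy is inert in one and effective in the other.

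**Step 3: precision of the difference.**

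- Standard error = SD × √(2/32) = 0.25 SD.
- 95% half-width = t(0.975; 62 df) × 0.25 SD = 2.00 × 0.25 SD = 0.50 SD. The normal approximation gives 1.96 × 0.25 = 0.49 SD.
- Difference detectable with 80% power = (1.96 + 0.84) × 0.25 SD = 0.70 SD.
- Power at a true difference of 0.5 SD = Φ(0.5/0.25 − 1.96) = Φ(0.04) = 52%.

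**Step 4: what a claim of no worse than standard would need.** With one-sided alpha of 0.025 and 80% power, n per arm = 2 × (1.96 + 0.84)² / margin², with the margin in SD units. Unrounded normal quantiles and rounding up give 33, 63 and 175 per arm for margins of 0.7, 0.5 and 0.3 SD. These margins are assumed. With 32 per arm, the trial falls just short at 0.7 SD and well short at the two smaller margins.

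**The case against.** The strongest reply is that this is one loosely worded sentence. The title, purpose and design description are all comparative, and in that setting the sentence can be read as a statement of how the two methods compared. It does not say that each method was judged against no treatment, or that both would be called effective. This stands as a plausible reading, and the design is valid for the comparative purpose. But on that reading the conclusion still rests on arm-level descriptives, with no stated contrast or interval, so the sentence needs the same correction.

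Several stronger inferences are tempting, and the documents do not support them:

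- *The plan treats equal times as proof that both methods work.* It contains no such rule. The wording permits that reading but does not commit to it.
- *The comparator is ineffective.* The rationale paragraph begins "Since the standard methods are not always effective and not suitable for all women who underwent a Caesarean delivery". Failing in some women is compatible with a useful average effect. The sound point is that no effect estimate for standard therapy is given.
- *Bowel function returns by itself, so arm means reflect natural recovery.* The document does not say this. It can be inferred from describing treatment as accelerating recovery, but Step 1 does not need it.
- *The trial can say nothing about standard therapy under any circumstances.* If the training arm did not receive standard care, a clearly faster standard arm would suggest that standard therapy works, provided Paula training does not slow recovery. That proviso comes from outside the trial's data.
- *The imprecision can be stated in hours.* No SD is given for any of the three events, so only the half-width in SD units can be derived.

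**Conclusion.** The point holds in a limited form. The trial identifies the difference between Paula training and standard care, not the separate efficacy of each, and the conclusion sentence does not respect that limit. The identification argument needs only the lack of an untreated reference.

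The size of the second part is a 95% half-width of about 0.5 SD, on the assumptions of 32 analysed women per arm and a common SD. If some events are not observed, the interval is wider. A result with similar means would leave differences of about half an SD in either direction unexcluded, so it could not be called equal efficacy.

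Whether the contrast is an added or a replacement effect cannot be settled from the text, and the interpretation of any result depends on it. The fault lies in the conclusion wording. Randomisation, arms and outcomes need not change. A reader should not infer that the comparative question is unanswerable or that a third arm is required.

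**What to change.** Replace the conclusion sentence in the data-analysis paragraph with text to this effect:

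> Conclusions will be based on the between-arm difference in time to each event (bowel sounds, flatus, defecation), reported with its 95% confidence interval. No conclusion will be drawn about standard therapy against no treatment. A result without a clear difference will be reported as inconclusive. It will not be presented as equivalence, or as evidence that the Paula Method is an effective alternative.

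Add one sentence to the design paragraph recording whether women in the training arm also received the standard measures. Name the contrast accordingly, as an added or a replacement effect.

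The cost is a few sentences, with no new patients or data. Because the text is written in the past tense, the same limits can be applied in the trial report. The downside is small: a less favourable claim if the two arms look alike.

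### Pain medication taken over the whole stay is correlated with the length of that stay, then called an effect and said to be confirmed by a t-test

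*Combined protocol and SAP*

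**What the plan says.** All of this is in the unnumbered text under the heading Protocol in the combined protocol and SAP.

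- **Data collection:** "information regarding pain medications used during the hospitalization and course of the admission were collected". No other period for medication use is given.
- **Analysis paragraph, last sentence:** "The effect of taking different types of pain medication on the duration of hospitalization in both groups was examined using the Pearson correlation", followed by the statement that "the results were confirmed by T-test".
- **Same paragraph, earlier:** the outputs are the bowel-function times "as well as frequency of postoperative complications in each group and other data". The next sentence reads "Based on these data, conclusions were drawn about the efficacy of the two intervention methods", and it comes before the medication sentence.
- **Design:** "The study included 64 women following elective Caesarean section" and "The participants were randomized on a 1:1 basis into a training group and a control group". The randomised factor is the exercise programme.

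The text does not say how medication use was coded, which groups the t-test compared, whether the arms were pooled or analysed separately, or what was adjusted for. It names no second data set.

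**The concern.** Three separate problems meet in one sentence.

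1. **Shared clock.** Medication use accumulates over the period whose length is the response. Extra days give extra chances to be counted as a user, so stay drives exposure even if no drug affects stay.
2. **Confounding.** Women were not randomised to pain medication. A complicated recovery can raise both drug use and stay. Complications were recorded, but the described analysis does not use them.
3. **Confirmation.** A second test on the same women over the same window inherits the same bias, so agreement between the two carries little or no independent information.

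At stake is a conclusion that pain medication prolongs stay, apparently supported by two tests, when the agreement could come from the shared window alone.

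**Working it through.** The plan gives no figure to reproduce for this analysis: no significance level, stay distribution or coding. From the documents come n = 64 and 1:1 allocation (32 per arm if exactly balanced). Everything else below is assumed, including a two-sided 0.05 level.

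**Step 1. Threshold.** Pearson is significant when |r| exceeds t/√(t² + n − 2). For n = 64, t = 1.999 and the threshold is 0.246. For n = 32, t = 2.042 and it is 0.349.

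**Step 2. Correlation expected with no drug effect.** Let stay be L days, and let a drug be given each day with probability h regardless of stay. With X the number of medication days, Cov(X, L) = h·Var(L) and Var(X) = h(1 − h)·E(L) + h²·Var(L), so

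r = √[ h·Var(L) / ((1 − h)·E(L) + h·Var(L)) ].

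With mean stay 4 days, SD 1 day and h = 0.3, r = √(0.3 / (2.8 + 0.3)) = 0.311, above the 0.246 threshold. Simulation of this setting gave mean r 0.311 and 71.5% false positives. Over SD 0.5 to 1.5 days and h from 0.1 to 0.6, false positives were 11%-100% for medication days and 10%-61% for any use (yes/no).

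**Step 3. Sensitivity to coding and to falling use.** Null simulation, n = 64, 10,000 runs per setting, stay 3 to 6 days (uniform, or weighted 20/60/15/5%):

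| Coding | Constant daily rate | Falls 30% a day | Halves daily | Falls 70% a day |
|---|---|---|---|---|
| Dose count (3 expected on day 1; between-woman log-SD 0 or 0.4) | 77%-100% | 21%-64% | 7%-13% | about 5% |
| Yes/no (first-day probability 0.1-0.5) | 12%-37% | 6%-9% | 5%-6% | about 5% |
| Number of types out of 4 (uniform stay; first-day probability 0.1-0.3) | 67%-89% | 13%-21% | 6%-7% | about 5% |

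With n = 32, dose counts gave 47%-100% at a constant rate, down to about 5%.

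**Step 4. Fixed window.** If exposure counts only the first two days and every woman stays at least that long, stay cannot add exposure and the covariance in Step 2 becomes zero. The simulated rate was 4.5%-5.7% across the n = 64 dose-count and yes/no settings. A repeat with 4,000 runs per setting gave 4.5%-6.2%.

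**Step 5. What the t-test adds.** For yes/no use, the equal-variance statistic is t = r·√((n − 2)/(1 − r²)), which is the Pearson test itself. In simulated data sets of 64 women the two p-values differed by no more than about 1e-14, which is rounding. Among 1,322 false positives (yes/no use, constant daily probability 0.2, uniform stay), the equal-variance t-test was also significant in 100% and Welch in 97%. For dose counts, a t-test of stay split at the median dose was also significant in 44% of false positives (halving) to 100% (constant rate). A t-test between the trial arms would answer a different question.

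**The case against.** The strongest reply has four parts.

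**The window is inferred.** The stay is named as the period of data collection, while the analysis sentence gives no window. That is so, but no earlier window appears anywhere, and a reader can only take the one stated.

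**The largest figures need a coding that the text does not suggest.** It speaks of types of drug, not doses. For yes/no use the inflation is modest once use falls over the stay. If women were grouped by main or first drug, a longer stay would give no extra chance of exposure and the shared clock would largely disappear. This stands as a limit on size: the bias in this trial is unknown and could be close to nil. Confounding remains under every coding, so *effect* is still unsupported.

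**The t-test may simply be the significance test of r.** That is a possible reading of loose wording. It makes the clause weaker still as confirmation, because no second analysis then exists. Deleting it loses nothing, since the correlation carries its own p-value.

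**Little depends on it.** Medication is not part of the stated purpose, the efficacy conclusions are tied to other data, and the document reports no finding that drugs prolong stay. This stands and limits the consequence to a secondary question.

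**Conclusion.** The concern holds. Two parts need no numerical assumption: an unadjusted correlation with a non-randomised exposure does not show an effect, and no available reading of the t-test makes it independent confirmation. The shared-clock bias follows from the stated window. Its size rests on assumed stay, coding and dosing patterns, and false-positive rates range from about the nominal 5% (steeply falling use) to 100% (dose counts at a constant rate). These figures show the direction and possible range of the bias, not its value in this trial. The correction should be made, but the randomised comparison of bowel-function times is untouched.

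**What to change.** - Replace *effect* with *association*, and label the analysis exploratory and non-randomised.
- Delete the clause saying that the t-test confirmed the result. If a t-test is reported, name its groups and do not present it as corroboration.
- State how medication use is coded: yes/no per drug, number of types, or dose count.
- If dose times were recorded, measure use in a fixed early post-operative window that every woman completes before discharge.
- If they were not, keep the correlation as description only, state the shared-window bias as a limitation, and draw no conclusion about medication affecting stay.

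The wording changes need no new data. The window needs dose times, and the documents do not say whether these exist. Its price is that later drug use no longer contributes. It removes the shared-clock bias but not confounding, so *association* is the right word either way.
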